### 12.1.3. Part 2 trial treatment for patients ineligible for durvalumab treatment

Patients who do not fulfil eligibility criteria above for durvalumab treatment, and who remain eligible for olaparib, should receive olaparib monotherapy for 12 months (13 cycles) during Part 2.

### 12.2. Obtaining Informed Consent for Trial Treatment in Part 2 - Cohorts F & G only

Patients allocated to Cohorts F and G should be invited to consent for PART 2 Trial Treatment using the Part 2 Trial Treatment Patient Information Sheet (PISs) and Informed Consent Form.

The PI (or delegated Co-investigator) must ensure that each trial participant is fully informed about trial treatment in Part 2 and possible risks involved.

At the WOP D14 visit, or sooner if preferred and only if Cohort allocation has been confirmed, the patient should be given the current ethics approved **PHOENIX Patient Information Sheet for PART 2 Trial Treatment** for their consideration and for subsequent discussion at the 30 day post-surgery visit.

Patients should only be asked to consent to PART 2 Trial Treatment at the 30 day post-surgical visit once they have had sufficient time to consider their participation, and had the opportunity to ask any further questions. For those patients who do go on to consent please refer to Section 13 for details of trial treatment and assessments.

Confirmation that the patient meets all Part 2 trial treatment eligibility criteria must be documented in the patient's medical notes by the PI (or delegated Co-investigator), along with confirmation of the patient's consent and the informed consent process for Part 2 trial treatment. One copy of the signed consent form PHOENIX Protocol Version: 10.0, 23 April 2025

IRAS Project Number: 249774

should be provided to the patient, one copy should be filed in the patient's medical records and the original should be retained in the SIF, which must be available for verification by the trial team at the ICR-CTSU or for regulatory inspection at any time.

Upon patient consent for trial treatment in PART 2 the **PART 2 Trial Treatment Form** must be completed. consent. Written confirmation that the patient has consented to trial treatment in PART 2 should also be documented in the patient's medical notes.

Patients must be logged centrally by the trials unit (ICR-CTSU) following consent to Part 2 trial treatment before trial treatment can commence. Please refer to the **PHOENIX Trial Guidance Notes** for the procedure to follow.

Patients can be logged for Part 2 trial treatment by ICR-CTSU from **09.00-17.00 (UK time) Monday to Friday**.

The following information will be required at confirmation of trial treatment in PART 2:

- Name of hospital, Investigator and person providing confirmation
- Confirmation that patient has given written informed consent for PART 2 trial treatment
- Patient's initials, date of birth and Trial ID

The ICR-CTSU Trial Team will send notification of confirmation of trial treatment in PART 2 to the site contact for the trial (Research Nurse/Trial Coordinator).

### 12.2.1. Non-consenting Patients from Cohorts F & G

Patients who do not consent to, or who are ineligible for, trial treatment in Part 2 should receive adjuvant treatment of Physician's Choice and followed up as described in Section 14.

# 12.3. Pembrolizumab treatment washout period requirement for patients eligible to receive durvalumab treatment in Part 2

Patients who are receiving pembrolizumab as part of standard of care, and who fulfil the eligibility criteria for durvalumab treatment in Part 2, should be asked to discontinue pembrolizumab only once consent to trial treatment in Part 2 has been obtained. The minimum washout period between last dose of pembrolizumab and Cycle 1 Day 1 of durvalumab is 30 days. Details relating to treatment with pembrolizumab, including date of last dose, will be captured in on the appropriate eCRF within the clinical database.

### 13.PART 2 TRIAL ASSESSMENTS: COHORTS F & G

# 13.1. Only patients allocated to Cohorts F and G who have consented to trial treatment in Part 2 can commence trial treatment post-surgery. PART 2 Pre-Treatment Assessments

The following pre-treatment assessments should be conducted once a patient has consented to trial treatment in Part 2.

The pre-treatment assessments should be performed prior to commencing trial treatment in PART 2 as indicated below:

### 13.1.1. Assessments to be conducted within 28 days prior to commencing treatment:

- ECG
- Pre-treatment conditions
- Assessment for any surgical complications including wound healing assessment

## 13.1.2. Assessments to be conducted within 3 days prior to Cycle 1 Day 1:

- Physical examination and vital signs (including weight, blood pressure, heart rate, temperature)
- ECOG performance status
- Review of concomitant medications
- Safety bloods: Haematology full blood count, white cell count with differential and ANC, prothrombin time and international normalised ratio (INR); Biochemistry sodium, potassium, calcium, magnesium, ALT, gamma-glutamyl transferase (GGT), bilirubin, albumin, creatinine, alkaline phosphatase, glucose, urea.
- Pregnancy test for women of childbearing potential

For patients who received pembrolizumab as SOC, and who discontinued this following consent to trial treatment in Part 2, the above assessments required within 3 days of Cycle 1 Day 1 should only be conducted once the required washout period of 30 days has been completed (see Section 12.3).

### Research blood sample collection:

• Research blood sample collection as specified in the PHOENIX Investigator Laboratory Manual. Please refer to Appendix 2 for further details on the sample collection requirements.

FOR DETAILS ON PART 2 TRIAL TREATMENT INCLUDING DOSE SCHEDULE, DOSE MODIFICATIONS, PERMISSIVE AND CONTRAINDICATED CONCOMITANT MEDICATIONS AND TOXICITY MANAGEMENT PLEASE REFER TO SECTION 25: PART 2 OLAPARIB & DURVALUMAB COMBINATION THERAPY.

### 13.2. PART 2 On-Treatment Assessments Cycle 2, Day 1 Pre-Treatment

The following assessments should be performed as close to as possible and within 3 days prior to treatment administration:

- Physical examination and vital signs (including weight, blood pressure, heart rate, temperature)
- ECOG performance status
- Dosing compliance
- Review of concomitant medications
- Safety bloods: Haematology full blood count, white cell count with differential and ANC, prothrombin time and international normalised ratio (INR); Biochemistry sodium, potassium, calcium, magnesium, ALT, gamma-glutamyl transferase (GGT), bilirubin, albumin, creatinine, alkaline phosphatase, glucose, urea. In addition for patients receiving durvalumab: TSH
- ECG
- Review of AEs
- Pregnancy test for women of childbearing potential

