16.8.1. Definitions

Potential Hy's Law (PHL)

PHOENIX Protocol Version: 10.0, 23 April 2025

71

IRAS Project Number: 249774

Aspartate aminotransferase (AST) or alanine aminotransferase (ALT)  $\geq$  3× upper limit of normal (ULN) **together with** total bilirubin (TBL)  $\geq$  2×ULN at any point during the trial following the start of trial treatment irrespective of an increase in alkaline phosphatase (ALP).

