### Hy's Law (HL)

AST or ALT  $\geq$  3 × ULN **together with** TBL  $\geq$  2 × ULN, where no other reason, other than trial treatment, can be found to explain the combination of increases, e.g., elevated ALP indicating cholestasis, viral hepatitis, another drug.

For PHL and HL the elevation in transaminases must precede or be coincident with (i.e., on the same day) the elevation in TBL, but there is no specified time frame within which the elevations in transaminases and TBL must occur.

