### 16.8.2. Evaluation of Potential Hy's Law (PHL) Cases

[figure not shown]
The patient should return to the participating site and be evaluated as soon as possible, preferably within 48 hours from awareness of the abnormal results. This evaluation should include laboratory tests, detailed history and physical assessment. In addition to repeating AST and ALT, laboratory tests should include albumin, creatine kinase, total bilirubin, direct and indirect bilirubin, gamma-glutamyl transferase (GGT), international normalized ratio (INR) and alkaline phosphatase. A detailed history, including relevant information, such as review of ethanol, recreational drug and supplement consumption, family history, sexual history, travel history, history of contact with a jaundiced patient, surgery, blood transfusion, history of liver or allergic disease, and work exposure, should be collected. Further testing for acute hepatitis A, B, or C infection and liver imaging (e.g. biliary tract) may be warranted. The possibility of progressive disease should be considered.

Potential Hy's Law (PHL) cases should be reported as SAEs (see Section 16.3).

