# **Hepatic toxicity**

Table C4. Cohort C hepatic toxicity management guidelines

Event	Actions
Grade 3 ALT/AST or Grade 3	• Withhold olaparib for up to 28 days until recovery to Grade ≤1 (or
bilirubin	Grade ≤2 in patients with Grade 2 ALT at baseline).
	Look for alternative causes.
	Reduce olaparib to the next dose reduction level.
	• If symptoms do not recover to Grade ≤1 (or Grade ≤2 in patients
	with Grade 2 ALT at baseline) within 28 days, discontinue olaparib.
Grade 4 ALT/AST or Grade 4	Permanently discontinue olaparib.
bilirubin	Evaluate alternative cause.

AST or ALT >3 x ULN	Withhold olaparib. Please refer to Section 16.8 for further
AND	information on evaluation and reporting requirements for potential

 
Total bilirubin >2 x ULN
 
	Hy's Law cases.
	• Evaluate the patient as soon as possible (within 48 hours if
	possible). All cases confirmed on repeat testing with no alternative
	explanation for abnormal liver function should be considered
	potential Hy's Law cases.
	Report as an SAE.
	Discontinue trial treatment if Hy's Law confirmed.
	If the criteria for Hy's Law are not met, follow the guidance above
	for Grade 3/4 ALT/AST or bilirubin.

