(HCC) patients (or secondary tumour involvement of the liver with abnormal baseline values [BLV])

ALT or AST >  $3 \le 5 x$ ULN or total bilirubin >  $1.5 \le 3 x$  ULN

- Hold study drug/study regimen dose until ALT or AST ≤ 3 x ULN or total bilirubin ≤ 1.5 x ULN. Resume study drug/study regimen after completion of steroid taper (<10 mg prednisone or equivalent).
- Permanently discontinue study drug/study regimen for any case meeting Hy's law laboratory criteria (AST or ALT >3 × ULN AND
- Regular and frequent checking of transaminases and total bilirubin (e.g., every 1 to 2 days) until transaminases and total bilirubin elevations improve or resolve.
- Consider checking creatinine phosphokinase (CPK) and aldolase (to rule out myositis)
- If no resolution to ALT or AST ≤ 3 x ULN or total bilirubin
   ≤ 1.5 x ULN in 1 to 2 days, consider discussing with
   Clinical Study Lead, as needed.

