	ALT or AST > 5- ≤ 10 x ULN  Concurrent ALT or AST > 3 x ULN and total bilirubin > 2 x ULN  ALT or AST > 10 x ULN OR total bilirubin > 3 x ULN	ALP) and in the absence of any alternative cause.  - Hold study drug/study regimen. Resume study drug/study regimen if elevations downgrade to ALT or AST ≤ 3 x ULN or total bilirubin ≤ 1.5 x ULN after completion of steroid taper (<10 mg prednisone, or equivalent).  - If in combination with tremelimumab, do not restart tremelimumab.  Permanently discontinue study drug/study regimen.	
 
Promptly initiate empiric IV methylprednisolone at 1 to 2 mg/kg/day or equivalent.
 
Check CPK and aldolase (to rule out myositis)
 
Perform Hepatology Consult, abdominal workup, and imaging as appropriate.
 
If still no improvement within 2 to 3 days despite 1 to 2 mg/kg/day methylprednisolone IV or equivalent, promptly start treatment with an additional immunosuppressant.(e.g., mycophenolate mofetil 0.5 – 1 g every 12 hours then taper in consultation with hepatology consult or relevant practice guidelines). Discuss with Clinical Study Lead if mycophenolate is not available. Infliximab should NOT be used.
 
Promptly initiate empiric IV methylprednisolone at 1 to 2 mg/kg/day or equivalent.
 
If still no improvement within 2 to 3 days despite 1 to 2 mg/kg/day methylprednisolone IV or equivalent, promptly start treatment with an additional immunosuppressant.(e.g., mycophenolate mofetil 0.5 – 1 g every 12 hours then taper in consultation with hepatology consult or relevant practice guidelines). Discuss with Clinical Study Lead if mycophenolate is not available. Infliximab should NOT be used.
 
Perform Hepatology Consult, abdominal workup, and imaging as appropriate.
 

Hepatitis	Any Elevations of	General Guidance	For Any Elevations Described
(elevated transaminases and total bilirubin)	AST, ALT, or T. Bili as  Described Below		
 
Patients should be thoroughly evaluated to rule out any alternative etiology (e.g., viral hepatitis, disease
 

Infliximab should not be used for management of immune-related	Described below		progression, concomitant medications, worsening of liver cirrhosis [e.g., portal vein thrombosis]).  - Monitor and evaluate AST, ALT, ALP, and T. Bili.

	- For hepatitis B (HBV) + patients: evaluate quantitative
	HBV viral load, quantitative Hepatitis B surface
	antigen (HBsAg), or Hepatitis B envelope antigen
	(HBeAg).

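### Part 2 safety bloods schedule ALT but not AST, although three liver-safety rules act on either enzyme, so an AST rise with ALT below threshold is not scheduled to be seen while bilirubin stays below its own action level

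*Protocol*

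**What the plan says.** **What is scheduled.** Protocol 13.2 lists the Cycle 2 Day 1 biochemistry as "Biochemistry sodium, potassium, calcium, magnesium, ALT, gamma-glutamyl transferase (GGT), bilirubin, albumin, creatinine, alkaline phosphatase, glucose, urea". The same analytes appear in 13.1.2 (pre-treatment), 13.3 (Cycle 3 onwards), 13.4 (discontinuation), 13.5 (30 days, and 90 days after durvalumab) and footnote 4 to the 13.8 schedule. From Cycle 2 onwards the lists add TSH for patients receiving durvalumab; nothing else changes by drug. Prothrombin time and INR are in the haematology part of each list.

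**What the rules act on.**
- Section 16.8.1 defines potential Hy's Law by "Aspartate aminotransferase (AST) or alanine aminotransferase (ALT") at or above 3 x ULN, together with total bilirubin at or above 2 x ULN. Section 16.8.2 makes such cases reportable as SAEs.
- Table C4 in 25.2.3 opens with "Grade 3 ALT/AST or Grade 3" bilirubin (withhold olaparib). Its Grade 4 row requires permanent discontinuation. A combined row covers AST or ALT above 3 x ULN with bilirubin above 2 x ULN. The caption still names Cohort C, but 25.2.3 sends Part 2 investigators to this table.
- The Appendix 7 hepatitis section has a hold row that starts at ALT or AST above 3 x ULN or bilirubin above 1.5 x ULN, and a combined row: "Concurrent ALT or AST > 3 x ULN and total bilirubin > 2 x ULN".

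**The concern.** A safety rule that can be met by AST alone needs an AST result. The protocol writes AST into three liver rules for Part 2 but into none of the panels that feed them. Where ALT stays below threshold and AST does not, the patient meets the transaminase part of a rule that says to withhold or stop a drug, or to report an SAE, and the scheduled bloods do not show it. At stake is the prompt recognition of a liver signal during up to 12 months of olaparib, with or without durvalumab. No efficacy conclusion is involved.

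**Working it through.** There is no figure in the plan to reproduce. The check sets the lists beside the rules.

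**Step 1: lists.** AST is named in 0 of the 6 Part 2 lists, and ALT in 6 of 6. The four Part 1 lists (11.1, 11.2, 11.4 and 11.5 footnote 3) have the same pattern: AST in 0 of 4. Identical wording in ten places makes a fault in text extraction implausible.

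**Step 2: rules.** All three liver rules (16.8.1, Table C4, Appendix 7) accept AST or ALT as the transaminase trigger.

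**Step 3: when does the missing AST matter?** Take a patient whose AST is over a rule's threshold and whose ALT is not, and vary bilirubin. The protocol grades by CTCAE v5.0 but does not print the boundaries. I assume that Grade 3 bilirubin begins above 3 x ULN when the baseline is normal. The Appendix 7 bilirubin rows also break at 3 x ULN.

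| Total bilirubin | Olaparib alone | Receiving durvalumab |
|---|---|---|
| Up to 1.5 x ULN | Grade 3 or 4 AST should lead to withholding or stopping olaparib; the scheduled panel shows no trigger | AST above 3 x ULN should lead to a hold under Appendix 7; the scheduled panel shows no trigger |
| Above 1.5, up to 2 x ULN | As above | Bilirubin alone reaches the hold row, which asks for "Regular and frequent checking of transaminases and total bilirubin (e.g., every 1 to 2 days"), so AST should be obtained |
| Above 2 x ULN, below Grade 3 (2 to 3 x ULN) | Bilirubin limb of the Hy's Law row is met; ALT does not meet the other limb, and AST has no routine result | Already held on bilirubin, with transaminases being checked |
| Grade 3 or above | Table C4 withholds (Grade 3) or stops (Grade 4) olaparib on bilirubin alone | The same for olaparib; durvalumab also acted on through bilirubin |

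**Step 4: reading the table.** The top row applies to every Part 2 patient. The two middle rows apply only to olaparib alone: patients ineligible for durvalumab (12.1.3), or continuing after durvalumab has stopped (25.1.2). In the bottom row the bilirubin rule acts without AST.

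**Step 5: how many patients?** At most 8 + 15 = 23 patients (Cohorts F and G) can receive Part 2 treatment. The documents give neither the frequency of AST rises with ALT below threshold nor the number who will take olaparib alone. No count of missed cases follows.

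**The case against.** The strongest reply is that ALT was a deliberate choice of marker. Table C4's recovery exception applies only "in patients with Grade 2 ALT at baseline", which fits an ALT panel. Every rule still works on ALT, and bilirubin, GGT, ALP and INR are drawn each time. Bilirubin alone stops treatment at Grade 3 or 4 in Table C4, and 25.2.4 interrupts olaparib for any Grade 3 or higher toxicity. Appendix 7 tells investigators to monitor AST in hepatitis. Trial Entry bloods (8.4) must confirm criteria that name AST. Sites may also add AST on their own initiative. All of this stands and narrows the gap. None of it is a scheduled on-treatment AST: the Appendix 7 text is event guidance without visit times, and Trial Entry comes before Part 2.

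It can also be said that the slash in Table C4's graded rows might not mean either enzyme. Either is the natural reading there, and 16.8.1, the combined row of Table C4 and Appendix 7 all say it outright.

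Four stronger readings are tempting, and the documents do not support them.
- *The timing rule defeats a late AST.* Section 16.8.1 says "the elevation in transaminases must precede or be coincident with (i.e., on the same day") as the bilirubin rise. But the same sentence sets no limit on the interval between the two rises. Table C4's combined row has no timing condition, so a later AST with bilirubin still raised meets it.
- *Part 2 eligibility cannot be confirmed.* The criterion in 12.1.1 joins the enzymes with a slash. If either suffices, the 13.1 bloods are enough.
- *The work-up proves that an earlier AST was assumed.* Section 16.8.2 says "In addition to repeating AST and ALT, laboratory tests should include albumin, creatine kinase". This mainly guarantees an AST once a case is suspected and is weak evidence of what was meant before that.
- *Only patients on olaparib alone are exposed.* With bilirubin at or below 1.5 x ULN, an isolated AST rise is unscheduled in durvalumab patients too.

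**Conclusion.** The mismatch is real, and its consequence is small. Followed to the letter, the Part 2 lists leave the AST limb of three stated liver rules without a scheduled measurement. The exposure is an AST rise with ALT below threshold while bilirubin is below its own action level: up to 1.5 x ULN with durvalumab, below Grade 3 on olaparib alone. For olaparib alone that includes the band from 2 to 3 x ULN, where a potential Hy's Law case could go unrecognised until someone orders AST.

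This rests on sites drawing exactly what is listed and on the assumed 3 x ULN boundary for Grade 3 bilirubin. Multiplying the omission by the number of visits would not measure harm. The Part 2 omission touches no endpoint or stopping rule: the adverse-event endpoint closes at 1 month after surgery (4.2), and Part 2 is descriptive (17.1.2). I am confident in the omission; how often it would matter is unknown. Minor severity, worth correcting because it is cheap.

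**What to change.** Add AST beside ALT in the six Part 2 safety-blood lists: 13.1.2, 13.2, 13.3, 13.4, 13.5 and 13.8 footnote 4. For consistency, make the same addition in the four Part 1 lists: 11.1, 11.2, 11.4 and 11.5 footnote 3. Leave the AST-or-ALT thresholds in 16.8.1, Table C4 and Appendix 7 as they are. The cost is one word in each of ten lists and one extra analyte on blood already drawn, with no added visit or sample.

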### **Research blood sample collection:**

 Research blood sample collection as specified in the PHOENIX Investigator Laboratory Manual (taken pre-dose for each cycle).

Please refer to Appendix 2 for further details on the sample collection requirements.

### 13.3. PART 2 On-Treatment Assessments Cycle 3 Onwards, Day 1 Pre-Treatment

The following assessments should be performed as close to as possible and within 3 days prior to treatment administration:

- Physical examination and vital signs (including weight, blood pressure, heart rate, temperature)
- ECOG performance status
- Dosing compliance
- Review of concomitant medications
- Safety bloods: Haematology full blood count, white cell count with differential and ANC, prothrombin time and international normalised ratio (INR); Biochemistry sodium, potassium, calcium, magnesium, ALT, gamma-glutamyl transferase (GGT), bilirubin, albumin, creatinine, alkaline phosphatase, glucose, urea. In addition for patients receiving durvalumab: TSH
- ECG
- Review of AEs
- Pregnancy test for women of childbearing potential

### Research blood sample collection:

 Research blood sample collection as specified in the PHOENIX Investigator Laboratory Manual (taken pre-dose for each cycle).

Please refer to Appendix 2 for further details on the sample collection requirements.

### 13.4. PART 2 Treatment Discontinuation Assessments

The following assessments should be performed at the time of discontinuation of trial treatment for any reason:

- Physical examination and vital signs (including weight, blood pressure, heart rate, temperature)
- ECOG performance status
- Dosing compliance
- Review of concomitant medications
- Safety bloods: Haematology full blood count, white cell count with differential and ANC, prothrombin time and international normalised ratio (INR); Biochemistry sodium, potassium, calcium, magnesium, ALT, gamma-glutamyl transferase (GGT), bilirubin, albumin, creatinine, alkaline phosphatase, glucose, urea. In addition for patients receiving durvalumab: TSH
- ECG
- Review of AEs

### Research blood sample collection:

 Research blood sample collection as specified in the PHOENIX Investigator Laboratory Manual.

IRAS Project Number: 249774

Please refer to Appendix 2 for further details on the sample collection requirements.

# 13.5. PART 2 30 Days (and 90 Days for patients receiving durvalumab) Post-Treatment Discontinuation Assessments

The following assessments should be performed 30 ( $\pm$  7) days (and 90 [ $\pm$  7] days for **patients receiving durvalumab**) post-treatment discontinuation:

- Physical examination and vital signs (including weight, blood pressure, heart rate, temperature)
- ECOG performance status
- Review of concomitant medications
- Safety bloods: Haematology full blood count, white cell count with differential and ANC, prothrombin time and international normalised ratio (INR); Biochemistry sodium, potassium, calcium, magnesium, ALT, gamma-glutamyl transferase (GGT), bilirubin, albumin, creatinine, alkaline phosphatase, glucose, urea. In addition for patients receiving durvalumab: TSH
- ECG
- Review of AEs
- Pregnancy test for women of childbearing potential (30 day post-treatment discontinuation visit only)

